The primary study outcome is to determine the feasibility of enrolling and randomizing AIS patients to a therapeutic intervention within less than one hour of ED presentation. Secondary outcomes of potential therapeutic effect to inform future clinical trial(s) include penumbral salvage at repeat imaging, change in NIHSS over the first 24 hours, and 3-month mRS. To assess potential adverse effects on markers of worsening stroke severity and possible hyperoxic lung injury, levels of MMP-9, IL-6, and IL-8 will be measured at initiation, 4 hours and 24 hours. Further analysis of additional biomarkers will be considered in the future.

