4.1. SUBJECT POPULATION

Eligible subjects will include acute ischemic stroke (AIS) patients aged 18 years or older who present to the UCH ED. There will be no specific selection of subjects based on sex, race or ethnicity, age, or socioeconomic status. We anticipate the study population to be representative of that of the greater Colorado Springs and Aurora, CO area with the exception that stroke prevalence increases with age and this will likely be reflected in the final study population.

Subjects with a suspected stroke who are normoxic at baseline (room air SpO₂≥94%) and have either 1) a target mismatch lesion on CT-perfusion [defined by RAPID automated software demonstrating a ratio of PWI_{Tmax>6} lesion volume/Infarct volume (with cerebral blood flow <30% normal) greater than 1.2 or 2) a non-contrast CT-head RAPID ASPECT score of 10 (suggesting a patient has not completed their infarct), a NIHSS≥ 1, and a LKW ≤ 12 hours will be screened for eligibility. While some vulnerable populations (i.e. children and prisoners) will be excluded, AIS by the nature of the disease has the potential to impair a subject's capability to give informed consent and places them in the category of a vulnerable population. All subjects will be evaluated for the ability to give informed consent through use of the University of California, San Diego, Brief Assessment of Capacity to Consent (UABCC) Form⁵³. In cases where the subject is determined to lack the ability to provide consent, the subject's legally authorized representative (LAR) will be approached. Consent forms describing in appropriate detail the study interventions, study procedures, and risks will

be given to the participant and/or their LAR. If and when the study subject regains capacity, they will be approached for continued participation. If the subject/LAR consents for participation he/she will sign the informed consent form prior to any study procedures being done.

In terms of potential pregnant women, it is anticipated that most women will be older than likely childbearing age. While supplemental oxygen use in pregnant women experiencing fetal distress is routine, the effects of maternal hyperoxia on a developing fetus are unknown. Those of likely childbearing potential will be excluded. If a subject withdraws for any reason from the study, he/she will be replaced to meet the enrollment goal when possible. Our target enrollment will be 200 patients (~100 per arm).

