4.2. INCLUSION / EXCLUSION CRITERIA

Inclusion Criteria: In order to be eligible to participate in this study, an individual must meet all of the following criteria:

1. Provision of signed and dated informed consent form from patient or legal authorized representative (LAR)
2. Subject or LAR stated willingness to comply with all study procedures and availability for the duration of the study
3. Males and female (of unlikely childbearing capacity) aged over 18 years
4. Exhibiting signs and physical examination findings suggestive of an acute ischemic infarction (with either):
 - a. A target mismatch profile of CT-perfusion or MRI determined by RAPID automated software to have a ratio of PWI_{T_{max}>6} lesion volume/DWI lesion volume >1.2 and NIHSS $\geq 1^{54}$
 - b. A RAPID automated software calculated non-contrast CT-head ASPECT score of 10 and LKW ≤ 12 hours (in patients with symptoms discovered upon waking, the LKW is defined at the midpoint between going to sleep and awakening based on previous studies that suggest most strokes during sleep occur close to awakening)⁵⁵
5. Normoxic; a pulse oximetry of 94% or greater at time of screening without the use of supplemental oxygen

Exclusion Criteria: An individual who meets any of the following criteria will be excluded from participation in this study:

1. Current use of supplemental oxygen
2. Prisoner
3. Pregnancy or those of likely childbearing potential (i.e. age <50, no documented negative pregnancy in last 24 hours, no documented history of hysterectomy)
4. Documented blood glucose <70mg/dL
5. Concurrent treatment with another investigational drug or other intervention
6. Documented history of any of the following chronic respiratory illness that require pulmonary vasodilators or supplemental oxygen at baseline: Chronic Obstructive Pulmonary Disorder (COPD), Emphysema, Interstitial Lung Disease, Restrictive Lung Disease, Pulmonary Hypertension, Pulmonary Fibrosis
7. Documented history of any of the following autoimmune diseases: systemic lupus erythematosus, rheumatoid arthritis, scleroderma, primary biliary cholangitis, multiple sclerosis, inflammatory bowel disease

8. Currently being treated for an acute myocardial infarction and/or decompensated heart failure at the onset of initial ED presentation as reported by the ED provider
9. Plans for treatment with either IV tPA (alteplase) or endovascular therapy

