In terms of effects on clinical patient outcomes, both the effect on 3-month mRS and NIHSS will be determined. The DEFUSE-3 study found the median NIHSS score in AIS patients evaluated for possible extended-window thrombectomy was 16 with an interquartile range of 10-20⁶³. Based on these results and our proposed sample size for feasibility and a 29% loss to follow-up, we will be able to detect a two-point difference in NIHSS between the hyperoxia and control groups at 24hours with 80% power and a type I error (α) of 0.05. Given the large potential number of confounding events between the time of study intervention and a 3-month mRS, this will be analyzed on an exploratory basis. The average 3-month mRS in both the hyperoxia and control groups will be compared. Finally, an exploratory analysis of the effects of hyperoxia on biomarkers of stroke severity and hyperoxic lung injury will be evaluated over time. The change in level of biomarkers (MMP-9, IL-6, and IL-8) over time will be analyzed and reported using the mean and standard deviation and will be depicted graphically.

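### The claim of 80% power for a two-point NIHSS difference rests on a thrombectomy-evaluation population not shown to match this trial, and does not follow from that population's own spread

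*Combined protocol and SAP*

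**What the plan says.** Section 17 introduces the NIHSS calculation with "The DEFUSE-3 study found the median NIHSS score in AIS patients evaluated for possible extended-window thrombectomy was 16" and an interquartile range of 10 to 20. Relying on that and on "our proposed sample size for feasibility and a 29% loss to follow-up", it concludes that "we will be able to detect a two-point difference in NIHSS between the hyperoxia and control groups at 24hours". The power is put at 80% and alpha at 0.05. It names no SD, test, sidedness or baseline correlation.

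Other sections bear on whether the source fits:

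- Section 4.2, exclusion 9, removes patients with "Plans for treatment with either IV tPA (alteplase) or endovascular therapy".
- Section 4.1 sets the severity floor: patients with "a NIHSS≥ 1, and a LKW ≤ 12 hours will be screened for eligibility". Section 4.2 repeats the NIHSS floor under the mismatch route only.
- There are two imaging routes in (Section 4.2, inclusion 4): a target mismatch with a ratio above 1.2, or a non-contrast CT with an ASPECT score of 10. Section 7, item 1a, says the mismatch criteria follow DEFUSE 3.
- Section 4 defines the secondary outcome as "change in NIHSS over the first 24 hours".
- Section 17 also says that the trial is not powered for secondary or exploratory outcomes.

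**The concern.** The only variability input for the NIHSS statement comes from patients being assessed for extended-window thrombectomy. Their lower quartile is 10, so about three quarters of them scored 10 or more. This trial admits patients from a score of 1 and excludes those with planned endovascular treatment or tPA. Nothing in the plan adjusts the source distribution or argues that it carries over.

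The quantity differs too. The source figure reads as a score at presentation, while the trial's outcome is a change over 24 hours. The spread of a change depends on the correlation between the two scores, which the plan does not give.

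The practical stake is modest. Section 4 says the secondary outcomes are to inform later trials, and this is one of two detectable differences that Section 17 gives for the planned sample size. A reader who takes 80% power for two points at face value will think the NIHSS comparison more precise than the plan's own inputs allow.

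**Working it through.** **Inputs from the documents.** Target enrolment 200, about 100 per arm (Section 4.1); 1:1 allocation (Section 7); 29% loss, power 80%, alpha 0.05, difference two points, interquartile range 10 to 20 (Section 17). **Assumed:** two-sided test, equal loss in both arms, comparison of two means, normal-theory conversion of the interquartile range.

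**Step 1: evaluable number.** 100 × (1 − 0.29) = 71 per arm.

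**Step 2: SD implied by the source.** (20 − 10) / 1.349 = 7.41.

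**Step 3: try to reproduce the two points.** Detectable difference = SD × (1.960 + 0.842) × √(2/n).

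- The same formula reproduces the plan's infarct-growth figure: 41 × 2.802 × √(2/80) = 18.2, against a stated 18%. So the method appears to be the plan's own.
- For NIHSS: 7.41 × 2.802 × √(2/71) = 3.49 points (3.51 with the t-distribution). Two points is not reproduced.
- Power for two points at SD 7.41 and 71 per arm is 36%. Two points at 80% power would need 216 evaluable per arm, or 216 / 0.71 ≈ 305 enrolled per arm.

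**Step 4: variants.**

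- One-sided alpha: 3.09 points.
- No loss at all (100 per arm): 2.94 points.
- Adjusting for baseline, SD × √(1 − ρ²): two points needs ρ of about 0.82. With a simple change score, SD × √(2(1 − ρ)), it needs about 0.84. Neither is stated.
- SD taken as half the interquartile range (5) with 100 per arm and no loss: 1.98 points, but this drops the stated 29% loss.
- SD 6 with 142 per arm gives two points, but 142 is the evaluable total of both arms (200 × 0.71). That this explains the 29% is only a guess.

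**Step 5: SD that the claim needs.** At 71 per arm the t-test requires a standardised difference of 0.473, so SD = 2 / 0.473 = 4.2.

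**Step 6: dependence on the unknown SD.** The documents give no NIHSS SD for eligible patients. SDs of 4 to 6 are assumptions; 7.4 is the value implied by the source.

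| SD | Power for 2 points | Detectable difference (0.473 × SD) |
|---|---|---|
| 4 | 84% | 1.9 |
| 5 | 66% | 2.4 |
| 6 | 51% | 2.8 |
| 7.4 | 36% | 3.5 |

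**The case against.** The plan disclaims power for secondary outcomes and describes its sample size as one chosen for feasibility. No sample size, analysis or decision rule depends on the NIHSS sentence. That stands and keeps the severity low. It does not make the sentence right, because the plan goes on to assert 80% power for one of those outcomes.

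The population contrast has limits. A reader might infer that exclusion 9 removes most of the source population, that the control arm is therefore mild, and that the NIHSS figure is wrong for this trial in a known direction. The documents do not support that:

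- Exclusion 9 applies to patients with treatment planned, while the source is patients evaluated for it. Those evaluated but not planned for treatment stay eligible, and their share is not given.
- The mismatch route uses DEFUSE 3-based criteria, so part of the sample is selected on imaging much as the source was.
- NIHSS 1 is a floor with no ceiling. Section 4.1 treats an ASPECT score of 10 as a sign that the infarct is not complete, not as a sign of mild deficit.
- The median of 16 does not enter a comparison of two means; only the spread does. A population with an SD near 4 would give 84% power, and the stated claim would hold.

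What remains is that the source is not shown to fit, and that the stated figure does not follow from it.

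A reader might also infer that a later trial would inherit two points as its target. The plan presents two points as detectable, not as a target, and a later trial could use the NIHSS results observed here.

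**Conclusion.** The point holds in two parts. First, the plan gives no ground for applying the spread of thrombectomy-evaluation scores to the 24-hour change in this trial's subjects, and the direction of any error is unknown. Second, and checkable, the fixed claim does not follow from its own inputs: power for two points is 36% where 80% is stated, and the detectable difference is about 3.5 points where 2 is stated.

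These figures rest on a two-sided, equal-variance comparison of means, 29% loss in each arm, and an SD of 7.4 read from the interquartile range under normality. They show what the cited source implies; they are not an estimate of this trial's actual power, which depends on an SD the documents do not give. Severity is low, because NIHSS is a secondary outcome.

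**What to change.** Rewrite the NIHSS part of Section 17:

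- Remove the fixed statement of 80% power for two points.
- State the detectable difference for the outcome defined in Section 4 as 0.47 × SD at 71 evaluable per arm (two-sided alpha 0.05, 80% power): 1.9, 2.4, 2.8 and 3.5 points at SD 4, 5, 6 and 7.4.
- Say which SD this is: that of the 24-hour change or, if the analysis adjusts for baseline, the residual SD. A raw-score SD would not be the right input for an adjusted analysis. Name the test and its sidedness.
- Say that the thrombectomy-evaluation spread is only a rough guide to this population.
- Commit to reporting the observed SD and a confidence interval for the treatment difference at the end of the trial, for use in planning a later one.

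The same edit corrects both the arithmetic and the choice of source, so they are best handled together. The cost is one rewritten paragraph and the loss of a single headline power figure in favour of a conditional one. The sample size does not change.

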7. STUDY PROCEDURES

As part of the screening and enrollment process, patients with suspected AIS will have either a non-contrast CT head with RAPID calculation of ASPECT score or a CT-perfusion head. Using standard stroke alert treatment protocols at this institution, the RAPID software is used in most potential stroke patients at our institution and will be used to calculate infarct and penumbral volume and targeted diffusion/perfusion mismatch for this study. As part of the screening process, medical charts and EMS reports will be accessed by study personnel as needed to ensure potential subjects meet all inclusion/exclusion criteria. The screening and enrollment procedures along with collection of initial vitals will occur almost simultaneously given the very acute nature of the presentation and desired short interval from ED presentation to randomization. No data will be collected during the screening process that is not part of routine patient care prior to subject enrollment. Routine patient demographics, past medical history, medications, and prehospital assessments will be obtained from chart review. No research data that is not already part of routine patient care will be entered into the subject medical records. Randomization will occur in a 1:1 fashion between the two treatment groups. The estimated study duration is 30 months to allow for full enrollment of subjects and the 3-month mRS assessment. Each subject will be followed for a total of 90 days from enrollment to final assessment. No results from this study will be shared with subjects.

[figure not shown]
Once consented and enrolled in the study, subjects will have the following procedures: (See Table 1 for Schedule of Activities).

1. *Infarct progression:*

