17. DATA ANALYSIS PLAN

The primary endpoint of this study is feasibility. We hypothesize that the challenges of enrolling and randomizing AIS patients to a therapeutic intervention within less than one hour of ED presentation can be addressed. The number of potential subjects meeting the inclusion criteria and the relative rates of enrollment over time will be tracked. Additionally, the timing to enrollment and initiation of treatment intervention will be monitored. The primary endpoint of this study is feasibility as measured by the mean time from presentation to the ED to randomization and initiation of intervention. We hypothesize that we will be able to enroll, randomize and initiate treatment intervention in less than one hour for 80% of the enrolled subjects.

This study is not powered to detect significant differences in secondary or exploratory outcomes. However, analysis of secondary outcomes will occur both on an intention-to-treat and a per-protocol basis. Penumbral salvage will be reported as an average and as a standard deviation of the mean. We plan to enroll a total of 200 patients. Based on previous data that showed a decrease in the relative infarct volume growth (infarct volume at presentation/infarct volume at 4 hours) in patients treated with hyperoxia (87.8 +/-22%) compared to controls (149.1 +/- 41%)²⁹, 5 patients per arm would be needed to detect a similar difference with a power of 90% and type I error rate (α) of 0.05⁶². However, this effect was seen in a small study with less than 10 patients per treatment arm. Thus, such dramatic changes in infarct volume may not be expected, but even a smaller reduction in infarct volume will be clinically important as small reductions in infarct volume can have profound clinical effects if it is in a key cerebral territory. If you assume 20% of patients for some reason do not receive standard follow-up imaging to allow for calculation of infarct progression, a standard deviation of 41%, 80% power and α of 0.05, the proposed sample size will be able to detect an absolute difference in infarct volume growth of 18% between the control and hyperoxia.

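### The stated 80% power for a two-point NIHSS difference at 24 hours does not follow from the plan's own inputs, which give about 36%

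*Combined protocol and SAP*

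**What the plan says.** Section 17 (Data Analysis Plan) takes a median NIHSS of 16, with an interquartile range of 10 to 20, from a study of patients evaluated for extended-window thrombectomy. From that spread, "our proposed sample size for feasibility and a 29% loss to follow-up", it concludes that "we will be able to detect a two-point difference in NIHSS between the hyperoxia and control groups at 24hours with 80% power". Alpha is set at 0.05. The section gives no SD, names no test, does not say whether the test is one- or two-sided, and mentions no adjustment for baseline.

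Three other places bear on the claim:

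- Section 4.1 sets enrolment at 200, about 100 per arm, and Section 7 says "Randomization will occur in a 1:1 fashion between the two treatment groups".
- Section 4 lists the secondary outcomes as including "change in NIHSS over the first 24 hours, and 3-month mRS", so the endpoint is described there as a change rather than as a score at 24 hours.
- Earlier in Section 17: "This study is not powered to detect significant differences in secondary or exploratory outcomes". The same paragraph nevertheless says that "the proposed sample size will be able to detect an absolute difference in infarct volume growth of 18% between the control and hyperoxia", on an SD of 41%, 20% missing follow-up imaging and 80% power.

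**The concern.** An interquartile range of 10 points implies a wide spread, and 71 patients per arm is a modest number, so a two-point difference looked too small to be detectable with 80% power.

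At stake is how the NIHSS result will be read. The secondary outcomes are meant to inform a later trial. A reader who accepts the 80% figure could take a null 24-hour result as evidence against a two-point effect. If power is nearer 36%, a true effect of that size would be missed nearly two times in three.

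**Working it through.** **Inputs.** Enrolment is 200, randomised 1:1 (Sections 4.1 and 7). Loss is 29%, so 200 × 0.71 = 142 evaluable, or 71 per arm. Alpha is 0.05, the target power 80% and the difference 2 points (Section 17). The SD is not stated and has to be derived from the interquartile range of 10 to 20 around a median of 16.

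**Which convention the plan uses.** The neighbouring infarct-growth figure can be reproduced. With SD 41% and 100 × 0.80 = 80 per arm, the detectable difference is (z for alpha + z for power) × SD × √(2/n):

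- Two-sided: (1.960 + 0.842) × 41 × √(2/80) = 18.2% (18.3% by the t distribution), against a stated 18%.
- One-sided: (1.645 + 0.842) × 41 × √(2/80) = 16.1%.

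That figure therefore fits a two-sided, unadjusted, two-sample comparison with the correct per-arm number. I use the same convention for NIHSS and show one-sided results beside it.

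**SD from the interquartile range (normality assumed).**

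- Whole range: 10/1.349 = 7.41.
- Upper half: (20 − 16)/0.6745 = 5.93.
- Lower half: (16 − 10)/0.6745 = 8.90.

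**NIHSS at 71 per arm, central case.** The standard error is 7.41 × √(2/71) = 1.244. The power for 2 points is approximately Φ(2/1.244 − 1.960) = Φ(−0.35) = 36%. The detectable difference at 80% power is 2.802 × 1.244 = 3.49 points. The noncentral t gives 35.8% and 3.51 points. All cases by the noncentral t:

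| Setting | SD 5.93 | SD 7.41 | SD 8.90 |
|---|---|---|---|
| 71 per arm, two-sided: power for 2 points | 51% | 36% | 27% |
| 71 per arm, two-sided: detectable difference | 2.8 | 3.5 | 4.2 |
| 71 per arm, one-sided: power for 2 points | 64% | 48% | 38% |
| 71 per arm, one-sided: detectable difference | 2.5 | 3.1 | 3.7 |
| 100 per arm (no loss), two-sided: power for 2 points | 66% | 48% | 35% |
| Evaluable per arm for 2 points at 80%, two-sided | 139 | 217 | 312 |

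One-sided testing and no loss together give 60% at SD 7.41 (48% to 77% across the SDs), still below 80%.

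**What would give 80% at 71 per arm, two-sided.**

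- An SD of about 4.2.
- Adjustment for baseline, where the residual SD is SD × √(1 − r²). At SD 7.41 this needs r = √(1 − (4.22/7.41)²) = 0.82 (0.70 at SD 5.93, 0.88 at SD 8.90).
- A change score, with SD × √(2(1 − r)) if the spread is equal at both times. At SD 7.41 this needs r = 1 − (4.22/7.41)²/2 = 0.84.

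The plan states none of these.

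**Possible origin.** Two readings land near 80%: SD 6 with the total of 142 used as if it were per arm (79.9%), and SD 5 (half the interquartile range) with 100 per arm and the loss ignored (80.4%). Both are conjecture, and nothing here depends on either.

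**The case against.** Several points can be made for the plan.

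*Sidedness is not settled.* Section 17 also says 5 patients per arm would suffice at 90% power for 87.8 ± 22 against 149.1 ± 41. With a pooled SD of 32.9, the normal approximation gives 4.93 one-sided but 6.05 two-sided, so that figure fits a one-sided test. The plan's convention is therefore mixed. This stands, but one-sided power for NIHSS is still only 38% to 64%.

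*The endpoint may be a change score or be analysed with baseline adjustment.* Section 4 supports the first. A strong enough correlation could bring power to 80%, so 36% is not necessarily the power of the analysis finally run. This also stands. But no correlation or SD of change is given, so the claim cannot be derived from what is written.

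*The spread is borrowed and its conversion is approximate.* It comes from thrombectomy candidates, whereas Section 4.2 excludes patients planned for alteplase or endovascular therapy and, on the mismatch route, admits an NIHSS of 1 or more. The true 24-hour SD could differ. Half the interquartile range, SD 5, would give 66% two-sided and 77% one-sided at 71 per arm, so 27% to 51% is not a hard bound. This limits confidence in 3.5 points as a forecast. It does not rescue the stated figure, which the plan itself bases on that spread.

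*The disclaimer covers it.* Saying that a trial is not powered for secondary outcomes can mean that it was not sized for them, and a detectable difference may still be quoted. On that reading the statements are in tension rather than strictly contradictory. The disclaimer still does not correct a wrong number.

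**Conclusion.** The concern holds. On the plan's own inputs, an unadjusted two-sided comparison at 71 per arm has about 36% power for two NIHSS points, not 80%, and would detect about 3.5 points. Across the SDs implied by the two halves of the interquartile range, the figures are 27% to 51% and 2.8 to 4.2 points. They rest on a normal conversion of a range taken from another population and on no baseline adjustment. That the stated 80% cannot be reproduced is firm; the exact replacement value is less so.

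The practical weight is modest. The primary endpoint is feasibility, and neither the 200-patient target nor any decision rule uses the two-point figure. It should be corrected because it overstates what the trial can show on a named secondary outcome meant to guide the next trial.

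**What to change.** In Section 17, either delete the two-point statement or replace it with one that carries its assumptions, for example:

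> With 71 evaluable patients per arm (200 enrolled, 29% loss), two-sided alpha 0.05 and 80% power, an unadjusted two-sample t-test would detect about 3.5 NIHSS points at 24 hours if the SD is 7.4 (interquartile range/1.349), or 2.8 to 4.2 points for SDs of 5.9 to 8.9. The spread is taken from a different population, and the study was not sized for secondary outcomes.

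If the intended analysis is a change score or is adjusted for baseline NIHSS, compute the figure for that model and state the assumed correlation. With adjustment at SD 7.4, correlations of 0.5 and 0.7 give about 3.0 and 2.5 points. Deletion is the safer choice if no better source for the SD is available.

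The cost is one sentence and a less favourable number. The sample size does not change.
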